14.3 Selection of KOOS Threshold

As described by the ICRS Recommendation Document [11], the KOOS was developed in 1994-1995 as an extension of the WOMAC Osteoarthritis Index with the purpose of evaluating short-term and long-term symptoms and function in people with knee injury and OA. The KOOS includes 42 items in 5 separately scored subscales: Pain, Other Symptoms, Activities of Daily Living (ADL), Function in Sport and Recreation (Sport/Rec), and Knee-related Quality of Life (QOL). Each subscale is scored from 0 to 100 on a worst to best scale. Evidence supports the use of the KOOS for several orthopedic interventions such as autologous cartilage repair and microfracture, ACL reconstruction, meniscectomy, and total knee replacement. The KOOS has been used to evaluate other interventions, including tibial osteotomy, physical therapy, nutritional supplementation, and glucosamine supplementation. The KOOS is used in many large-scale databases, including the prospective registries on ACL reconstruction in Norway, Sweden, and Denmark; the MOON database in the United States; and the National Institutes of Health– sponsored Osteoarthritis Initiative following 5000 subjects at risk of OA, or with OA, for 5 years. Data from the latter study are freely available at www.oai.ucsf.edu. Normative data from the general population and from men and women having ACL reconstruction have been published.

In the reliability evaluation of the KOOS for people with articular cartilage lesions, test-retest was assessed over 2 days. The ICCs (Intraclass Correlation Coefficients) ranged from 0.87 to 0.95 for the 5 sub- scales, and the internal consistency ranged from 0.74 to 0.95. The minimal detectable change (MDC) for the Pain subscale was estimated to be equal to 6. When determining the effectiveness of an intervention, the proportion of individuals who achieve a minimal clinically important difference (MCID) should be considered. This was estimated to be 8-10 points for the KOOS subscales. Since the MDC is smaller than the MCID, it is shown that the KOOS Pain subscale has sufficient test-retest reliability to detect the suggested MCID. The MDC for the ADL subscale is 7.

The use of the KOOS Pain subscale in the primary composite clinical success endpoint, followed by the conditional testing of the KOOS ADL subscale is consistent with the ICRS Recommendation Document. “Although there is appeal in a single score for simplicity’s sake, reporting outcomes in separate sub-scales helps in interpreting the outcome of clinical studies and can assist subjects in their understanding of the expected course of their recovery over a number of outcomes”. “The recommended method for addressing such multiplicity issues is hierarchical testing of endpoints—that is, the primary endpoint is

tested first; if this is statistically significant, the secondary endpoint is tested, and so on. When an endpoint is statistically insignificant, no further endpoints are tested. The hierarchy of endpoints should of course be defined *a priori* and be described in the study protocol.”

14.4 Study Number Assignment

Subject ID number assignment is done when the subject has met study criteria, signed the informed consent form, scheduled a surgery date and Inclusion/Exclusion has been entered into the Electronic Data Capture System. The Subject ID number will be the first two digits of the site number followed by a three-digit patient number, automatically assigned by the Electronic Data Capture System after entering the Inclusion/Exclusion form. Informed consent may occur up to 90 days prior to or at the time of the study procedure, however all other enrollment criteria should be completed within 60 days. A Randomization ID will be assigned at the time of randomization just prior to the procedure.

14.5 Sample Size Determination

For testing the primary superiority hypothesis as defined above and assuming true CCS rates of 0.80 and 0.60 for S+A and AA, respectively, a total of 174 subjects (116 and 58, respectively) are need for 80% power. This value is increased by 15% to 201 to account for losses-to-follow-up (134 S+A and 67 AA).

14.6 Analysis of Secondary Endpoints

The following secondary endpoints will be examined:

- 1) Comparison of mean change in KOOS Pain, ADL, Symptoms, Sports and Recreation, Quality of Life Subscale scores
- 2) Longitudinal comparison of KOOS subscales over 12 to 24 months post-surgery
- 3) Comparison of mean Numeric Pain, EQ-5D and Global Satisfaction scores, where available
- 4) X-ray evaluation of joint space narrowing, osteophyte and cyst formation and subchondral sclerosis, where available
- 5) MRI analysis of bone marrow lesion variables, where available
- 6) Incidence and time to resolution of post-operative complications and adverse events
- 7) Incidence and time to joint injections, where available
- 8) Incidence and time to re-operations and revisions
- 9) Number of visits to healthcare providers, diagnostic or treatment procedures, and support devices; use of pain medication; and days of productivity lost, where available.

14.7 Safety Endpoints

Assessment of the safety profiles will be based on the incidence and seriousness of adverse events associated with the treatment.

Adverse event rates will be summarized by type of AE and for specific AEs in two ways:

- 1) Per subject using counts and percentages,
- 2) By event, summarizing event counts by visit interval over time.

Device and procedure related events will be summarized by seriousness. Events listings will be provided that include details such as relatedness, severity, onset and resolution status for all events and for relevant subsets of events such as serious events and related events.

Additional tables presenting a survey of the incidence rates by treatment groups will be drawn up for the following classifications and items:

- Premature Termination, Serious Adverse Events and Causal Relationship
- Separate Presentation of Serious Adverse Events

14.8 Analyses Populations

Subjects will be assigned a subject ID number after verification that they met the preliminary study criteria, have signed the informed consent form, scheduled a surgery date and Inclusion/Exclusion has been entered into the Electronic Data Capture System. A Randomization ID will be assigned just prior to the time of surgery.

The **intent-to-treat (ITT)** population is defined as subjects who complete the preoperative procedures and are randomized just prior to the time of surgery. The final determinations of inclusion and exclusion criteria and stratum assignment are made during surgery. The allowable exclusions will be any subject who does not meet inclusion or exclusion criteria based on surgeon review. Preoperative and surgical data will be collected from these subjects, along with the reason for the subject being excluded from the study. However, the subject will be exited and will not continue for follow-up. The baseline analyses and analyses of population characteristics will be performed on the ITT group.

The **modified ITT (mITT)** population is defined as subjects who meet all inclusion and exclusion criteria and have an arthroscopy with SCP or arthroscopy alone as outlined in Section 9.5. The modified ITT population will be used for the primary and secondary efficacy analyses and safety analyses.

The **per-protocol (PP)** population is all subjects who are assigned a study number, receive treatment as randomized per the study procedure and complete the study according to the protocol. Exclusions for the per-protocol analysis population include, but are not limited to, protocol violations and any actions that compromise the efficacy of the procedure. The primary variables analyses will be done on this population to determine if study findings would have differed with the inclusion of the excluded subjects.

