5.0 Introduction

5.1 Clinical Background

Subchondral bone defects, sometimes called bone marrow lesions (BMLs), are MRI-visible defects that can be seen on fat-suppressed MRI sequences (T2FS, PDFS, etc.) where they appear as a hazy white area against the background of darker bone. Pathologists have shown that BMLs represent a healing response to trauma such as micro trabecular fractures of the subchondral bone [1]. BML defects have been highly correlated with pain symptoms in the knee [2, 3]. However, BMLs and their impact on knee pain and function went relatively unrecognized in the orthopedic literature until 2011 [4].

Treatment options for BMLs have been limited in the past. For degenerative or chronic BMLs, treatments have included core decompression, extracorporeal shock wave therapy and pharmaceuticals [5]. While core decompression seeks to directly stimulate the bone through a surgical procedure, it does not fill the voids and defects in the bone and is not widely used to treat BMLs in the knee. Subchondroplasty® is a procedure first described in 2007 to fill subchondral osseous defects associated with bone marrow lesions using an injectable bone substitute material (BSM), AccuFill® [6]. AccuFill is an injectable, self-

setting, macro-porous, osteo-conductive, calcium phosphate bone graft substitute material that is intended for use to fill bony voids or gaps of the skeletal system of the extremities, spine (i.e. posterolateral spine), and the pelvis that are not intrinsic to the stability of the bony structure. These defects may be surgically created osseous defects or osseous defects created from traumatic injury to the bone. AccuFill is a bone graft substitute that resorbs and is replaced with new bone during the healing process. AccuFill has unique properties that allow it to flow through the osseous defects in trabecular bone and then set up hard at body temperature [7]. Two year results from a clinical study on 66 subjects considering TKA has shown improvements in subject reported pain and function with only 30% of subjects undergoing revision to TKA at 2 years [8]. The goal of this study is to evaluate the clinical outcomes associated with the on-label use of AccuFill during the Subchondroplasty procedure with arthroscopy compared to arthroscopy alone in subjects with bone marrow lesions in the knee.

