7.0 Study Design

This is a multicenter, prospective, single-blinded, two-arm, randomized study. Enrolled subjects will have a single BML of the tibia, single BML of the femur, or adjoining BMLs of tibia and femur, as long as the BMLs are in the same compartment of the knee. Subjects will also be surgical candidates for knee arthroscopy due to mechanical symptoms, meniscus tear, loose body and/or synovitis.

A stratified blocked randomization will be used to assign subjects to either Subchondroplasty with arthroscopy or to arthroscopy alone in a 2:1 ratio. Individual sets of blocks will be determined within study site and lesion polarity status (unipolar vs bipolar).

Subjects will be consented within 90 days prior to surgery and take part in follow-up visits for two years following surgery. A preoperative visit (with exception of MR imaging) will occur within 60 days prior to surgery. Telephone follow-up interviews will be done at 6 weeks, 3 months, 6 months, 9 months, 18 months and 24 months post-surgery. Target enrollment is 201 subjects, to include 134 subjects in the treatment group (SCP + Arthroscopy) and 67 subjects in the control group (Arthroscopy alone).

Enrollment was stopped early when an interim analysis demonstrated that the study was unlikely to meet its primary endpoint due to an unexpectedly high success rate in the arthroscopy only group. Follow-up will continue for all subjects enrolled through the 24 month visit to allow further monitoring of outcomes related to revisions, reoperations, adverse events, and to collect KOOS assessments and numeric pain scores.

Subjects will complete the study at the 24 month follow-up visit. For the purposes of this protocol, a revision will be defined as any partial or total joint arthroplasty or any bone fixation, bone grafting or bone substitute procedure in the same compartment in the study knee.

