9.4 Randomization Procedures

The surgeon will be blinded to the treatment group until the time of surgery to avoid potential selection bias during the screening process. The subject will be blinded to the treatment group throughout the study. The research coordinator will input the subject's Inclusion/Exclusion criteria into the Electronic Data Capture System, once all criteria has been confirmed, and select that the subject is ready to randomize when appropriate. Subjects may be randomized prior to surgery to allow for OR set-up. However, randomization should be performed as close to the time of surgery as possible to reduce the risk of randomization failures due to cancelled procedures.

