14.10 Poolability, Stratified Analyses, and Covariates

Site poolability will be evaluated using a random effects meta-analysis approach using the R package metafor to implement the analysis. True effects are assumed to be normally distributed with mean μ and variance τ^2 .

By imposing a specified distribution on the site-to-site variability, i.e. a normal distribution with mean μ and variance τ^2 , sensitivity to small sample sizes in individual sites is reduced and the parameters reflecting the magnitude of site-to-site variability are naturally derived. The quantitative measure of the magnitude of heterogeneity is I^2 . I^2 is the fraction of τ^2 that is due to effect size heterogeneity, as opposed to sampling variance. Fractions 25% and less are considered small. If there is significant site to site variability, the impact on this variability will be evaluated using a random effects logistic regression.

Primary endpoints and selected secondary endpoints will be subjected to stratified analyses in order to evaluate poolability and heterogeneity of device group differences. Stratifications will include age (<55 vs ≥ 55 years), gender, body mass index (<30 vs ≥ 30 kg/m²), femoral vs tibial primary lesion, and unipolar vs bipolar lesion polarity status.

Analyses will focus on determining if clinically significant group differences exist for variables that potentially have important associations with clinical outcomes.

Identification of such variables will be based on clinical significance and not statistical significance since the study was not powered to detect any specific magnitude of difference between randomized groups. Nonetheless, conventional p-values for baseline group differences will be provided for descriptive purposes only and as a visual aid in identifying covariates worthy of further consideration. Variables for which clinically significant group differences are observed that are also associated with outcomes will be utilized as covariates in supporting analyses design to characterize how relative efficacy may vary

across subgroups. Additionally, using data from the investigational device only, a failure risk analysis will be performed starting with the same set of baseline covariates with the possible addition of procedure and device specific variables.

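### Section 14.8 makes the lesion-polarity stratum final during surgery, after randomisation, so the polarity analyses in 14.10 could rest on a label that depends on the arm

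*Combined protocol and SAP*

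**What the plan says.** Section 7.0 sets up the stratified blocked 2:1 randomisation: "Individual sets of blocks will be determined within study site and lesion polarity status (unipolar vs bipolar". The Section 3.0 synopsis says the same.

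On timing, Section 14.8 states: "A Randomization ID will be assigned just prior to the time of surgery". Section 9.4 allows it to be earlier: "Subjects may be randomized prior to surgery to allow for OR set-up". On blinding, Section 9.4 states: "The surgeon will be blinded to the treatment group until the time of surgery to avoid potential selection bias during the screening process".

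The lesions are characterised before any of this. Section 5.1 says that bone marrow lesions "are MRI-visible defects that can be seen on fat-suppressed MRI sequences". Inclusion criteria 6 and 7 in Section 8.1 require MRI confirmation and a single lesion or adjoining tibial and femoral lesions.

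Section 14.8 then says, of the intent-to-treat population: "The final determinations of inclusion and exclusion criteria and stratum assignment are made during surgery".

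Section 14.10 subjects the primary and selected secondary endpoints to stratified analyses. Its list of factors ends with "femoral vs tibial primary lesion, and unipolar vs bipolar lesion polarity status". It does not say whether polarity is the value used at randomisation or the value settled in surgery.

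**The concern.** A stratification factor protects a comparison because it is fixed before allocation. Here the factor has to exist before randomisation, since the blocks are built within it, yet the plan calls its assignment final at a later point. By then the allocation exists and the surgeon's blinding is ending or has ended. No section requires the stratum to be settled before the arm is known, or by someone blinded to it.

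If the surgical value goes into the 14.10 analysis, the unipolar and bipolar groups may be defined partly by something that happened after allocation. A within-stratum difference could then reflect who was relabelled rather than what the treatment did. Section 14.10 also takes forward as covariates those variables that differ between arms and are associated with outcome. Relabelling in one arm could create such a difference in a factor that randomisation had balanced. All of this concerns subjects who stay in the analysis. Who is removed on surgical review is a separate question.

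**Working it through.** **1. Which part of the stratum can change.** The strata are site and polarity (Section 7.0). Site is fixed, so a final stratum assignment made in surgery can alter only polarity.

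**2. Order of events.**
- Polarity is available from the preoperative MRI (Section 8.1, criteria 6 and 7; Section 9.3).
- Randomisation within polarity takes place just before surgery or earlier (Sections 9.4, 14.4 and 14.8).
- The surgeon's blinding lasts until the time of surgery (Section 9.4). Subchondroplasty may come before or after the arthroscopy (Section 9.5.2), so the arm can be known before any arthroscopic finding.
- Stratum assignment becomes final during surgery (Section 14.8).

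That the arm is known when the stratum is settled is a strong inference from this order. It is not stated outright.

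**3. The plan's own sample size, and whether it is touched.** Section 14.5 assumes CCS rates of 0.80 and 0.60 with 80% power. The figure of 174 is reproduced with one-sided alpha 0.04, 2:1 allocation, pooled variance and a continuity correction:
- Pooled rate = (0.60 + 2 × 0.80)/3 = 0.7333.
- Uncorrected AA (arthroscopy alone) n = [1.7507 × √(0.7333 × 0.2667 × 1.5) + 0.8416 × √(0.24 + 0.16/2)]² / 0.20² = 50.7.
- Corrected AA n = (50.7/4) × [1 + √(1 + 6/(2 × 50.7 × 0.20))]² = 58.0. This gives 58 AA and 116 S+A (Subchondroplasty with arthroscopy), 174 in total.
- 174 × 1.15 = 200.1, which becomes 201 (134 + 67).

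No stratum enters this calculation. Section 14.2 describes the CCS test as a one-sided normal approximation and names no stratum term.

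**4. Possible size in the unipolar stratum.** The documents give no inputs for this, so the following are assumptions. Let *b* be the bipolar share, *u* and *v* the success rates in unipolar and bipolar subjects (the same in both arms, so no treatment effect), and *r* the fraction of one arm's bipolar subjects relabelled unipolar, chosen without regard to outcome. The unipolar rate in that arm becomes

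[(1 − b)u + b·r·v] / [(1 − b) + b·r].

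The other arm stays at *u*.

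| Arm relabelled | b | u | v | r | Unipolar rate in that arm | False S+A minus AA difference |
|---|---|---|---|---|---|---|
| S+A | 0.30 | 0.75 | 0.55 | 0.1 | 0.5415/0.73 = 0.742 | −0.8 points |
| S+A | 0.30 | 0.75 | 0.55 | 0.3 | 0.5745/0.79 = 0.727 | −2.3 points |
| S+A | 0.30 | 0.75 | 0.55 | 0.5 | 0.6075/0.85 = 0.715 | −3.5 points |
| AA | 0.30 | 0.75 | 0.50 | 0.1 | 0.540/0.73 = 0.740 | +1.0 points |
| AA | 0.30 | 0.75 | 0.50 | 0.2 | 0.555/0.76 = 0.730 | +2.0 points |
| AA | 0.30 | 0.75 | 0.50 | 0.3 | 0.570/0.79 = 0.722 | +2.8 points |

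The overall rate in each arm does not move: 0.7 × 0.75 + 0.3 × 0.55 = 0.69 in the first set and 0.7 × 0.75 + 0.3 × 0.50 = 0.675 in the second. In the first set the apparent bipolar share of S+A falls from 30% to 0.3 × (1 − r) = 27%, 21% and 15%. That is the kind of imbalance that could bring polarity into the covariate analyses.

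**5. Against sampling error.** At full enrolment the unipolar stratum would hold about 0.7 × 134 = 94 and 0.7 × 67 = 47 subjects. The standard error of the difference is √[0.75 × 0.25 × (1/94 + 1/47)] = 0.077, or 7.7 points. Every shift in the table is less than half of that.

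**The case against.** The strongest reply is that this is an ambiguity with little consequence. Lesions are identified on preoperative MRI, so polarity may rarely change in surgery. Section 14.10 does not say that the surgical value is the one analysed. Polarity enters the analysis only as one of five stratifications for poolability and heterogeneity, and possibly as a covariate; no confirmatory test uses it. The illustrative shifts are small against sampling error, and since enrolment stopped early (Section 7.0) the real standard error is larger than 7.7 points. A value frozen at randomisation also keeps any entry errors made then. All of this stands, and it limits the point to supportive analyses. It does not remove the rule in 14.8, which calls the surgical assignment final and so invites its use.

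A reader might infer four stronger things that the documents do not support:
- That a bipolar S+A subject with only one lesion injected becomes unipolar while AA subjects keep their MRI label. No section defines polarity by lesions injected. Section 9.5.2 speaks of filling the area or areas of the lesions, and the 14.8 determination is not limited to one arm.
- That the balance from stratified randomisation is lost and the polarity contrast is biased. Balance is created at allocation; relabelling can disturb it within subgroups only, and bias arises only if the surgical value is used and relabelling differs between arms.
- That the primary result is compromised. The CCS test has no stratum term.
- That the femoral or tibial location of the primary lesion has the same fault. It is not a randomisation stratum, and no section says it is settled in surgery.

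**Conclusion.** The point holds as a defect in a stated rule with limited reach. Under Section 14.8 the final polarity label is a post-randomisation value that can depend on the arm. The unipolar/bipolar analysis in 14.10, and any covariate use of polarity, could be biased if that value is used. The CCS tests at 12 and 24 months, the alpha split, the power and the sample size are unaffected.

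The distortion is probably small: about 1 to 3.5 points in the unipolar stratum, with the sign set by which arm is relabelled. That range rests on an assumed 30% bipolar share, assumed success rates, relabelling of 10% to 50% of bipolar subjects in one arm only, and relabelling unrelated to outcome among bipolar subjects. The conclusion also rests on two inferences: that stratum assignment in 14.8 means polarity, and that the surgeon may know the arm when it is settled.

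**What to change.** In Section 14.8, delete the words *and stratum assignment* from the sentence on determinations made during surgery. In Section 14.10, state that every polarity analysis, stratified or adjusted, uses the value recorded at randomisation from the preoperative MRI. Report any later correction of polarity, including intraoperative findings, only descriptively by arm or as a sensitivity analysis.

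The cost is one edit in 14.8 and one sentence in 14.10. The value should already be held, because randomisation within polarity requires it, although Section 9.4 mentions only the entry of eligibility criteria. The small downside is that preoperative entry errors remain in the main polarity analysis; the sensitivity analysis covers that. The change is still useful with enrolment closed, because it governs analysis and alters no study procedure.

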10.4.2 Surgical Reoperation or Revision

A reoperation of the index knee or revision of the SCP injection site may be performed at the discretion of the Investigator (e.g., due to progressive pain or disability, clinical or radiographic evidence of potential graft failure, etc.). A reoperation is defined as any surgical procedure on the index knee. For the

purposes of this protocol, a revision will be defined as any partial or total joint arthroplasty or any bone fixation, bone grafting or bone substitute procedure in the same compartment in the study knee.

The investigator is to dictate detailed operative notes that include the measures listed below, or have paper copies of the Surgical Reoperation Form completed during surgery to serve as a source document.

10.4.3 *Surgical Reoperation Documentation*

- Reason for Surgery
- Postoperative Diagnosis
- OR Time
- Anesthesia Type

All reoperations should be documented on an Adverse Event Form and the surgery documented on the Surgical Reoperation Form.

In the event that a revision occurs (defined as any partial or total joint arthroplasty or any bone fixation, bone grafting or bone substitute procedure in the same compartment in the index knee), the subject will be excluded from any future per protocol (PP) analysis of secondary endpoints, but should continue to be followed through the two-year endpoint for ITT analysis. An Adverse Event Form and Surgical Reoperation Form will be completed.

In the event that a reoperation occurs that does not involve revision of the BML site(s), an Adverse Event Form and Surgical Reoperation Form will be completed, and the subject will continue to be followed in the study per protocol. If possible, reoperations should not be performed within 6 weeks of the 12 and 24 month visits.

10.4.4 *Subject Cross-over Between Treatment Groups*

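### The primary (mITT) population can lose randomised subjects through eligibility decisions made during surgery, when the surgeon may know the arm, and no planned analysis brings them back

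*Combined protocol and SAP*

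**What the plan says.** **Randomisation (9.4).** The coordinator enters the eligibility criteria, "once all criteria has been confirmed, and select that the subject is ready to randomize when appropriate". Allocation can precede the operation: "Subjects may be randomized prior to surgery to allow for OR set-up". On blinding: "The surgeon will be blinded to the treatment group until the time of surgery to avoid potential selection bias during the screening process". Only the subject stays blinded throughout.

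**Final eligibility (14.8).** "The final determinations of inclusion and exclusion criteria and stratum assignment are made during surgery". The decision-maker is the surgeon: "The allowable exclusions will be any subject who does not meet inclusion or exclusion criteria based on surgeon review". Preoperative and surgical data and the reason for exclusion are kept. "However, the subject will be exited and will not continue for follow-up".

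**Populations (14.8).** The mITT keeps only those who satisfy every eligibility criterion and actually undergo one of the two procedures described in 9.5. It carries the primary and secondary efficacy analyses and the safety analyses. ITT is assigned only the baseline and population-characteristics analyses. The per-protocol set adds further restrictions.

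**Missing data (14.9).** The tipping-point grid is for mITT subjects without an evaluable CCS. Multiple imputation, triggered when more than 10% of data are missing, aims to include all mITT subjects.

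**The concern.** Excluding a randomised subject is harmless when the decision is blind to arm or rests on facts fixed before allocation. Neither safeguard is written into 14.8. No text withholds the allocation until eligibility is final, and no blinded or independent review of the exclusion is described. By contrast, 10.4.5 requires independent blinded review before cross-over.

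If subjects with a poor outlook were excluded more readily in one arm, the mITT success rate in that arm would rise for reasons unrelated to treatment. The excluded subjects have no postoperative outcome and sit outside every efficacy and sensitivity analysis, so the report could not show whether this had happened. The superiority claim on CCS, and the conditional ADL test behind it, would rest on a comparison whose integrity cannot be checked.

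**Working it through.** **1. Trace an excluded subject through the plan.**

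| Analysis | Population | Includes subjects excluded during surgery? |
|---|---|---|
| Baseline and characteristics | ITT | Yes, as 14.8 appears to intend |
| Primary CCS, conditional ADL, secondary, safety | mITT | No |
| Tipping point | mITT, CCS not evaluable | No |
| Multiple imputation | mITT | No |
| Per-protocol | Narrower still | No |

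Section 14.8 says the per-protocol analysis will show whether findings would have differed had excluded subjects been included. A more restricted set cannot show that for subjects lost before mITT.

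**2. Reproduce the plan's sample size, to fix the test and numbers.** Inputs from 14.2 and 14.5: rates 0.80 and 0.60, allocation 2:1, one-sided test, 80% power. Section 14.5 gives neither alpha nor any continuity correction; I tried alpha 0.04 with a correction.
- Pooled rate: (0.60 + 2 × 0.80)/3 = 0.7333.
- AA size before correction: [1.7507 × √(1.5 × 0.7333 × 0.2667) + 0.8416 × √(0.24 + 0.16/2)]² / 0.20² = (0.948 + 0.476)²/0.04 ≈ 50.7.
- With correction: (50.7/4) × [1 + √(1 + 6/(50.7 × 2 × 0.20))]² ≈ 58.
- Total: 58 + 116 = 174, matching the plan.

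**3. Effect of selective exclusion on the observed rate.** The documents give no exclusion rate, so the following are assumptions: no true effect, success 0.60 in both arms, a fraction f excluded from S+A only, and success p_e among those excluded.

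Observed S+A rate = (0.60 − f × p_e)/(1 − f).

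**4. Effect on type I error.** I enumerated the one-sided pooled z test exactly over two binomials with 116 and 58 evaluable, at the month-24 alpha of 0.04. With no exclusions the error is 0.041.

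| f | p_e | Observed S+A rate | Shift (points) | Type I error |
|---|---|---|---|---|
| 2% | 0.4 | 0.604 | 0.4 | 0.046 |
| 2% | 0.2 | 0.608 | 0.8 | 0.051 |
| 5% | 0.4 | (0.60 − 0.02)/0.95 = 0.6105 | 1.1 | 0.054 |
| 5% | 0.2 | (0.60 − 0.01)/0.95 = 0.6211 | 2.1 | 0.071 |
| 10% | 0.4 | (0.60 − 0.04)/0.90 = 0.6222 | 2.2 | 0.073 |
| 10% | 0.2 | (0.60 − 0.02)/0.90 = 0.6444 | 4.4 | 0.123 |

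**5. Vary the assumption about arms, with the same test.**
- 5% excluded from S+A and 2.5% from AA: 0.048 to 0.055.
- 5% excluded from both arms with the same p_e: about 0.041, so no inflation.
- 5% excluded from AA only: the formula raises the AA rate instead, and the error falls to 0.030 (p_e 0.4) or 0.022 (p_e 0.2). The bias then runs against S+A.

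**6. Sensitivity to the background rate.** The protocol reports unexpectedly high success with arthroscopy alone. With 134 and 67 randomised, 7 exclusions from S+A (5%) and excluded subjects having from half the usual success rate down to none, the error is 0.065 to 0.099 at a true rate of 0.60 and 0.091 to 0.176 at 0.80.

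**The case against.** **The surgeon's knowledge of the arm is inferred.** Section 9.4 ends blinding at the time of surgery but does not place disclosure before or after the final eligibility check. A reader might infer that the surgeon always knows the arm when excluding. The documents support only that the surgeon may know. This stands.

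**Exclusions are probably few.** Section 9.4 has all criteria confirmed before randomisation. Osteoarthritis grade, alignment and lesion presence come from preoperative imaging, and most other criteria are history or preoperative scores. Worse cartilage than expected is recorded under 9.5.3 and is not in itself an exclusion. The criteria that could plausibly change in the operating room are few, such as ligament stability, subchondral collapse, or an indication for an excluded concomitant procedure. This stands and makes the higher exclusion fractions less likely. It does not close the route, because 14.8 treats the earlier check as preliminary.

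**Two nearby inconsistencies do not affect the primary p-value.** A reader might infer that setting the stratum during surgery distorts the primary test, but 14.2 describes an unstratified normal approximation; polarity enters only the supporting analyses in 14.10. A reader might also infer that 10.4.3 and 10.4.6 promise an ITT efficacy analysis, since subjects "should continue to be followed through the two-year endpoint for ITT analysis". Those sections concern revised or unblinded subjects, who remain in mITT and are followed. That is a terminology mismatch and loses nobody.

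**A false positive is less likely in practice.** Enrolment stopped because the interim analysis found the primary endpoint unlikely to be met. That lowers the practical risk and makes 116 and 58 illustrative, but it does not make the population definition sound.

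**Conclusion.** The gap in the plan is clear from its text. Randomised subjects can be removed from the primary population during surgery, by a surgeon who may know the arm. They are not followed, and no planned analysis restores them. The comparison is open to selection bias; the documents do not show that bias occurred.

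A reader might go further and conclude that blinding during screening achieves nothing or that the randomised comparison is lost. Neither follows. Blinding still protects screening, and if exclusions are absent, or unrelated to arm or prognosis, the comparison is intact.

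The size depends wholly on assumed exclusion rates. With exclusions confined to S+A and a success rate of 0.60, the 0.04 test runs at about 0.054 to 0.071 for 5% excluded and 0.07 to 0.12 for 10%. Balanced exclusion gives no inflation, and exclusion confined to AA makes the test conservative. This is a should-fix point: confidence is high in the gap and low in any particular amount of bias.

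**What to change.** - **14.8 and 14.9:** analyse CCS in all randomised subjects, as randomised. Say plainly that this set includes subjects excluded during surgery. Treat their outcomes as missing, include them in the tipping-point grid, and include them in multiple imputation where it is triggered. Note that imputation will have only their baseline and surgical data, so the grid is the more informative part.
- **Reporting:** present this analysis beside the mITT result and require any superiority conclusion to be read against it.
- **Table:** list intra-operative exclusions by arm with reasons. The reasons are already collected under 14.8, and 14.7 already plans a premature-termination table by group.
- **Stratum:** use the polarity stratum entered at randomisation in any stratified analysis.
- **Consistency:** reconcile 9.4 (criteria confirmed before randomisation) with 14.8 (final determination during surgery), and align the ITT wording in 10.4.3 and 10.4.6 with the population actually used.

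The cost is SAP wording, a few more missing outcomes and slight dilution of the effect estimate. Recruitment ended in November 2020, so any exclusions have already happened, but 17.3 starts the final analysis only after data lock, which leaves room to specify this beforehand. If the table shows no exclusions, the added analysis has no such subjects to restore and the doubt is removed.
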